3. PRIMARY ESTIMAND

Primary Estimand		
Primary scientific question of interest	What is the optimal dose of LEVI-04 compared to placebo in participants with knee OA?	
Target Population	Defined through appropriate inclusion/exclusion criteria as listed in the study protocol.	
Treatments of Interest	LEVI-04 intravenous infusion dose 0.3 mg/kg LEVI-04 intravenous infusion dose 1.0 mg/kg LEVI-04 intravenous infusion dose 2.0 mg/kg	
Outcome Variable	Change in WOMAC pain subscale score from Randomization (Visit 3) to Visit 10 (week 17)	
Summary Measure	Least square mean difference between active doses and placebo and associated p-values from ANCOVA model with fixed effects for treatment, and covariates site and Baseline WOMAC pain subscale score, adjusting for multiplicity using Dunnett's step-down procedure.	
Intercurrent Events	Discontinuations due to:	

4. STATISTICAL METHODOLOGY

4.1 General Principles

All collected study data will be presented in listings. All derivations and statistical analyses will be performed using SAS® software Version 9.4. Prior and concomitant medications will be coded using the current version of the World Health Organization (WHO) Drug Dictionary available at the start of the study and will be used for the duration of the study even if a newer version of the dictionary is released. Similarly, adverse events (AEs) and medical history will be coded using the current version of the Medical Dictionary for Regulatory Activities (MedDRA) available at the start of the study and will be used for the duration of the study.

Unless stated otherwise, descriptive summaries for continuous variables will include n (number of participants with non-missing results), mean, standard deviation (SD), median, minimum, and

LEVI-04-21-02 Statistical Analysis Plan	Version: Final 3.0
Date: 18-Mar-2024	Page 14 of 34

maximum. For categorical variables, n and percent will be provided. Percentages will be calculated out of the number of participants in the given population with a non-missing result.

Nominal outcome summaries, presented by collection day and/or by time point, will be based on scheduled assessments as planned in the protocol. Unscheduled assessments will be presented in listings and will not be included in the analyses except for determination of Baseline as described in Section 5.1. All other visit and time point collections will be as recorded on the electronic case report forms (eCRFs).

WOMAC subscale scores will be standardized to a range of 0 to 10. Imputation of missing WOMAC pain subscale scores described in Section 4.9 will be based on the original score range. Standardization will occur after imputation at the time of analysis. Listings will present the original scores.

The primary analysis will be conducted once data collection associated with this analysis has been completed. That is, no additional data will be collected that would affect the results of the primary analysis despite the study being ongoing.

Unless otherwise stated, hypothesis testing will be two-sided with an alpha level of 0.05.

4.2 Randomization

The screening/randomization procedure will be centrally managed through an electronic Interactive Web Responding System (IWRS) integrated in the EDC system. To enroll and randomize a new participant, the Investigator/authorized personnel will have to access the EDC system by entering their username and password and filling in the requested data. Randomization will be centrally balanced across the study (not by center).

A total of approximately 416 participants are planned to be randomized in a 1:1:1:1 to the placebo and three active arms. If needed based on the interim conditional power analysis, the sample size will increase up to 624.

4.3 Sample Size Considerations

This study is planned to enroll approximately 416 participants, with a possibility of adding an additional 208 participants pending a conditional power analysis done at the interim analysis. It is assumed that there is a minimum effect of 10 out of 100 in change from baseline in WOMAC pain subscale score for at least one of dose groups compared with placebo, and a standard deviation of 19.2 for change from baseline. Dropout rate is assumed to be 15%, distributed evenly over the study duration of the study. An interim analysis (IA) will be conducted when approximately 208

LEVI-04-21-02 Statistical Analysis Plan	Version: Final 3.0
Date: 18-Mar-2024	Page 15 of 34

participants have completed the Week 5 visit. Based on the IA's conditional power analysis, the study will continue as planned with a total of 416 participants randomized, or with an increase of up to 208 participants (an additional 50%) up to a total of 624 participants. The final analysis will be conducted between the three treatment arms and placebo using a simple combination test with weights of 1/2 on the interim Z and 1/2 on the final Z, using a Dunnett's test. With this design, the power for a statistically significant difference between at least one active treatment group versus placebo assuming the study will continue to at least the originally planned sample size is:

	nario: treat	tment mean	Power with sample size of 416	Increase of sample size to 624 at the interim analysis		
Arm 1	Arm 2	Arm 3	SD=19.2	SD=22 SD=23 SD=24		SD=24
10	7.5	5	90%	94%	92%	90%
10	5	2.5	88%	92%	89%	86%
10	0	0	86%	91%	88%	85%

4.4 Multiplicity Adjustment and Sample Size Reassessment

Dunnett's step-down multiple comparison procedure will be used to compare the three active arms to placebo. Dunnett adjusted p-values for three comparisons will be determined initially (equivalent to a two-sided type-1 error of approximately 0.0188 for each comparison) to maintain an overall two-sided type-1 error of 0.05. If any of the three comparisons is found to be significant (adjusted two-sided p-value ≤ 0.05), the remaining two comparisons will be made using Dunnett adjusted p-values for two comparisons (equivalent to a two-sided type 1 error of approximately 0.0270 for each comparison). If either one is significant (adjusted two-sided p-value ≤ 0.05), the last comparison will be made at a two-sided 0.05 level of significance.

In order to protect the overall type-1 error given the sample size recalculation, a simple combination test will be used to combine the statistics for each treatment comparison from the interim and post-interim data, assigning 1/2 weight to the interim Z-value, and 1/2 to the post-interim Z-value (i.e., the Z-value of the post-interim participants are calculated from the participants not included in the interim analysis). The final Z-value will be calculated as: $Z = Z_1 \left(\frac{1}{2}\right)^{0.5} + Z_2 \left(\frac{1}{2}\right)^{0.5}$ where Z_1 is the interim Z-value, and Z_2 is the Z-value calculated on participants not included in the interim analysis. Z-values for the comparisons of each dose group

LEVI-04-21-02 Statistical Analysis Plan	Version: Final 3.0
Date: 18-Mar-2024	Page 16 of 34

to placebo for the interim and post interim participants will be calculated by transforming the onesided p-values (obtained from the ANCOVA one-sided t-statistics) for each comparison to onesided Z-values.

4.5 Analysis Sets

The Intention-to-Treat Analysis Set

The Intent-to-Treat (ITT) Analysis Set will include all participants randomly allocated to a treatment, based on the intention to treat "as randomized" principle (i.e., the planned treatment regimen rather than the actual treatment given in case of any difference).

Modified Intention-to-Treat Analysis Set

The Modified Intention-to-Treat (mITT) Analysis Set will include all participants from the ITT Analysis Set who have a baseline and at least one post-treatment WOMAC pain subscale score assessment available.

Per-Protocol Analysis Set

The Per-Protocol (PP) Analysis Set will include all participants from the mITT Analysis Set who have been treated according to the trial protocol and fulfill the following criteria:

- Absence of major clinical trial protocol deviations with respect to factors likely to affect the efficacy of the treatment.
- Adequate compliance with trial medication: participants must have at least four study drug administrations, including an administration at Week 16.

Protocol deviations will be reviewed prior to unblinding to determine which, if any, participants are to be excluded from the Per-Protocol Analysis Set.

Safety Analysis Set

The Safety Analysis Set will include all participants who have been administered at least one dose of trial treatment. Participants will be analyzed according to the actual treatment they receive.

LEVI-04-21-02 Statistical Analysis Plan	Version: Final 3.0
Date: 18-Mar-2024	Page 17 of 34

4.6 Participant Disposition

The number of participants screened and the number of participants not continuing beyond screening and the reason why will be summarized overall. The number of participants in each of the analysis sets will be summarized by treatment, site, and overall, where applicable.

The number and percentage of participants who completed the study will be presented by treatment, and overall for the ITT Analysis Set. Frequency and percentage of participants who withdrew or discontinued from the study and the primary reason for withdrawal, will also be summarized by treatment and overall.

4.7 Participant Demographics and Baseline Characteristics

Demographic data and participant characteristics at Baseline will be summarized descriptively. Medical history will be presented by MedDRA system organ class (SOC) and preferred term (PT).

4.8 Prior and Concomitant Medications

Prior and concomitant medications are classified as follows.

- A prior medication is any medication taken prior to the first dose of study drug.
- A concomitant medication, (i.e., concomitant with study drug) is any medication taken on or after the first dose of study drug.

A medication may be classified as both prior and concomitant. When determining prior or concomitant status for a medication, in the event that the start or end dates of the medication are unknown or incomplete, the medication will be considered as prior and concomitant unless the non-missing date information, if any, is enough to conclude that the medication could not be prior or, separately, could not be concomitant. Incidence of prior and concomitant medication use, according to medications collected on the prior/concomitant medication CRF page (i.e., excluding rescue medications from the rescue medication dispensing and accountability CRFs), will be summarized by World Health Organization (WHO) Drug dictionary coded terms Anatomical Therapeutic Chemical (ATC) classification and preferred name (PN).

4.9 Missing data

The WOMAC osteoarthritis index is a self-administered questionnaire consisting of 24 items divided into three subscales: pain (5 items), stiffness (2 items), and physical function (17 items). Scores for the subscales are based on the sum of the responses (each ranging from 0, no symptoms, to 10, worst imaginable) within the subscale. If participants fail to complete all questions, then missing responses will be imputed as the mean of the non-missing responses within the same subscale provided that:

LEVI-04-21-02 Statistical Analysis Plan	Version: Final 3.0
Date: 18-Mar-2024	Page 18 of 34

- Pain Subscale: no more than one response is missing,
- Stiffness Subscale: no more than one response is missing,
- Function Subscale: no more than three responses are missing.

If the number of missing responses for a given subscale meets the specified criterion, then the overall score for the subscale is calculated according to the non-missing and imputed responses and considered as an observed response. If more than the specified number of responses is missing, the subscale is considered invalid and the subscale score is considered missing. All non-missing responses will be presented in listings regardless of the number of missing responses.

Missing data for the primary endpoint (WOMAC pain subscale score) will be imputed using multiple imputations (MI) methodology. All missing visits data will be imputed using all prior visits data as well as treatment. Data that is missing at random will be imputed using the randomized treatment assignment, whereas data that is missing due to treatment (adverse event, lack of efficacy) will be imputed using placebo as the treatment. For the MI model, 100 imputations will be generated using PROC MI of SAS®. Fully conditional specification (FCS) model using the regression method will be used with non-missing baseline and post-baseline WOMAC pain subscale, and other important covariates to impute any missing data including missed visits and missing data due to dropouts. The seed to be used is 20220420. The results from the MI will then be used to derive the value of the change from baseline in the WOMAC pain subscale score at each timepoint, and then analyzed using the analysis of covariance (ANCOVA) model. The results of the 100 analyses will be transformed into a normal statistic and combined into a single analysis using PROC MIANALYZE.

Missing WOMAC pain subscale scores will be imputed as described above at the time of the interim analysis. This imputation will be used only for the interim analysis. Missing scores will be imputed again at the end of the study for all participants in the study, including those that were included in the interim analysis using all available data at the end of the study. Both the interim and end of study imputations will be based on the same methodology and seed. Participants may be ongoing in the trial at the time of the interim analysis, so they may have a missing Week 17 score at the time of the interim analysis and a non-missing score at the end of the study. With the inclusion of the post-interim analysis participants and additional collections for some of the interim participants at the end of the study, the analysis results at the end of the study for participants included in the interim analysis may differ from the results observed at the time of the interim analysis.

The Boston Carpal Tunnel Questionnaire (BCTQ) is a measure of self-reported severity of symptoms and functional status associated with carpal tunnel syndrome. The questionnaire

LEVI-04-21-02 Statistical Analysis Plan	Version: Final 3.0
Date: 18-Mar-2024	Page 19 of 34

consists of a Symptom Severity subscale (11 items) assessing severity of wrist or hand pain, change of sensation, and weakness in hand or wrist the past two weeks and a Functional Status subscale (8 items) assessing ability to perform various hand/wrist related tasks. Overall scores for the subscales are based on the average of the responses within the subscale. Individual missing responses will be imputed as the average of the non-missing responses. The average score of a subscale will not be calculated if more than one response is missing.

Survey for Autonomic Symptoms is a two-part questionnaire comprising 11 (for females) or 12 (for males) items, validated for assessing autonomic symptoms. For each item the participant will be asked if he/she have had the symptom the last 6 months (Yes/No) and, if Yes, how much would they say the symptom bothered them on a score ranging from 1 ("Not at all") to 5 ("A lot"). The overall score will be calculated as the sum of the responses, where "No" is scored as "0" and "Yes" responses are analyzed according to the score associated with how much the symptom bothered them. The number of participants with exactly one, exactly two, or three or more symptoms will be summarized. For the sum, individual missing responses will be imputed as the average of the non-missing responses. The average score will not be calculated if more than one response is missing. For the summary of the number of symptoms, missing responses will not be imputed. Participants with more than one missing response will be excluded from the number of symptoms summary unless the participant has checked "Yes" for three or more of the non-missing system responses.

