- 8. Planned major surgery or other major invasive procedures while participating in the study
- 9. Surgery or stent placement for coronary artery disease in the six months prior to screening
- 10. Nondiagnostic arthroscopy performed on the target knee joint within 180 days prior to Screening; or diagnostic arthroscopy performed on the target knee joint within 90 days prior to Screening
- 11. Intraarticular injection therapies to the target knee joint within 12 weeks prior to Screening, or to any non-target major joint within 6 weeks prior to Screening
- 12. Participants likely to be deemed unfit for joint replacement surgery due to concomitant illness, in the investigator opinion
- 13. Opioid use, including Tramadol, of 4 or more instances per week over the month prior to Screening
- 14. Known history of hypersensitivity to monoclonal antibodies
- 15. Presence of any medical condition or unstable health status that, in the judgment of the investigator, might adversely impact the safety of the participant or efficacy results of the trial
- 16. Medical history and/or clinical findings (including ECG) of cardiac disease that in the opinion of the investigator are considered of clinical significance, including but not limited to established ischemic heart disease, peripheral arterial disease and /or cerebrovascular disease (unstable angina, myocardial infarction, cardiovascular thrombotic events, transient

Version

Version 3.0_07FEB2023

ischemic attacks, and stroke are considered clinically significant if time of event occured within six months prior to screening)

- 17. Active malignancy or history of malignancy within the past 5 years, with exception of resected and cured basal cell carcinoma and squamous cell carcinoma of the skin
- 18. Clinically significant abnormal laboratory parameter(s) and/or electrocardiogram (ECG) parameter(s) during Screening, that, in the judgment of the Investigator, would preclude the participant from participation in this study
- 19. Participation in other studies involving investigational drug(s) within 30 days (or 90 days for biologics) prior to screening
- 20. History of Carpal Tunnel Syndrome with signs or symptoms within one year of Screening or a Boston Carpal Tunnel questionnaire (Symptom Severity Scale mean score ≥3)
- 21. Total score on Number of Symptoms (Column Q1a) on the SAS >3
- 22. Pregnant or breast feeding
- 23. Previously received any form of anti-Nerve Growth Factor (NGF)

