7.9.3 Survey for Autonomic Symptoms

The Survey of Autonomic Symptoms consists of two columns with two separate scores: A "Number of symptoms score" and a "Total symptom impact score". The first score refers to the total score from column Q1a where the participant answers Y/N to if he/she has had the specific symptom the last 6 months. Yes counts as 1 point, No as 0 and total score for the Number of symptoms score ranges from 0-11 (males) and 0-12 (females). The "Total symptom impact score" is the total score from the second column, Q1b and is scored on impact of the symptoms the participant answered yes to having, ranging from 1 ("not bothered by this symptom") to 5 ("bothered a lot") (total score range 0-60)¹⁸. Both column Q1a and Q1b are to be completed. The Number of symptoms (Q1a) score will be used to determine eligibility, with exclusion of participants with a score of > 3 (4 or more).

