4.14 Additional Questionnaire Analyses

The BCTQ and the Survey for Autonomic Symptoms results will be summarized for the ITT Analysis Set using observed data only. Change from baseline in the average Symptom Severity subscale scores and average Functional status subscale scores for the BCTQ will be summarized by treatment and visit. Frequency and percentage of participants reporting at least 1, 2, or 3 symptoms according to the Survey for Autonomic Symptoms will be summarized by gender, treatment, and visit. The change from baseline in total symptom impact score according to the Survey for Autonomic Symptoms will be summarized by gender, treatment, and visit. No formal testing will be performed on the BCTQ or the Survey for Autonomic Symptoms results.

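### The symptom-count table for the Survey of Autonomic Symptoms tops out at three, the highest count allowed at entry, so it cannot show worsening in participants who enter with exactly three; the item counts by sex are also reversed between protocol and SAP (minor)

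*SAP*

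**What the plan says.** **Entry limit.** Protocol 5.2.3, exclusion 21, excludes on "Total score on Number of Symptoms (Column Q1a) on the SAS >3". Protocol 7.9.3 repeats the rule, "with exclusion of participants with a score of > 3 (4 or more"). The highest count allowed at entry is therefore 3.

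**Count summary.** SAP 4.9: "The number of participants with exactly one, exactly two, or three or more symptoms will be summarized". SAP 4.14 gives it as "Frequency and percentage of participants reporting at least 1, 2, or 3 symptoms", by gender, treatment and visit. The first set of categories is exclusive and the second is cumulative. Neither goes above 3.

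**Impact score.** SAP 4.14 also plans the change from baseline in the total impact score, split the same way. Each symptom answered Yes scores 1 to 5 for bother and each No scores 0. Protocol 7.9.3 gives the range as 0-60.

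**Items by sex.** Protocol 7.9.3: "total score for the Number of symptoms score ranges from 0-11 (males) and 0-12 (females"). SAP 4.9: a "two-part questionnaire comprising 11 (for females) or 12 (for males) items".

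**Timing and status.** The survey is completed at screening, Week 8 and Week 20 (protocol Table 1). SAP 4.14 plans no formal testing of it.

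**The concern.** Both documents (protocol 3.2, SAP 1) report that adverse effects on the sympathetic nervous system raised safety concerns for anti-NGF antibodies, and LEVI-04 acts on the same pathway. The events of special interest in protocol 9.1.9 cover sensory and neuropathic events and joint events; none is specifically autonomic. The survey is thus the trial's dedicated autonomic instrument.

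The top category of its count table begins at the highest count an eligible participant may have. That category mixes participants who entered with 3 and stayed there with participants who went past the trial's own exclusion threshold during treatment. No planned table gives the number in the second group.

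As background only, the amendment log in protocol Appendix II records that version 3.0 raised the cut-off to admit a score of 3, citing emerging screening data. This suggests that such people were being seen, but gives no number.

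Two drafting conflicts affect the same analysis: the category definitions differ between SAP 4.9 and 4.14, and the documents disagree on which sex has 12 items, although the results are reported by sex.

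**Working it through.** **Inputs.** Highest entry count 3 (protocol exclusion 21 and 7.9.3). Top category 3 or more (SAP 4.9, 4.14). Items: 11 for one sex and 12 for the other (both documents, with the sexes reversed). Bother 1 to 5 per symptom present, 0 if absent (protocol 7.9.3, SAP 4.9).

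**1. The plan's own figure.** Maximum impact score = items x 5. With 12 items, 12 x 5 = 60, which matches the protocol's 0-60. With 11 items, 11 x 5 = 55. The stated range fits 12 items for one sex but does not show which.

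**2. Which rises change category.** Let the category be c(k) = min(k, 3) for a count k. From baseline b with n items there are n - b possible higher counts. A rise shows only if c(k) > c(b).

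| Baseline count | Possible rises, 11 items | Change category | Possible rises, 12 items | Change category |
|---|---|---|---|---|
| 0 | 11 | 11 | 12 | 12 |
| 1 | 10 | 10 | 11 | 11 |
| 2 | 9 | 9 | 10 | 10 |
| 3 | 8 | 0 | 9 | 0 |

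The cumulative version behaves the same way: a participant with 3 symptoms is already counted under at least 1, at least 2 and at least 3.

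**3. With a category of 4 or more.** Now c(k) = min(k, 4), and from a baseline of 3 the visible rises are 8 of 8 and 9 of 9. No eligible participant is in this category at screening, so anyone in it later has passed the entry limit.

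**4. What the impact score adds.** With bother on the existing symptoms unchanged, going from 3 to 4 symptoms adds 1 to 5 points, and from 3 to 6 adds 3 to 15. The score can therefore register the rise. Two assumed cases show its limits:

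- If 10% of an arm went from 3 to 6 symptoms and nothing else changed, the arm mean would rise by 0.10 x 3 = 0.3 to 0.10 x 15 = 1.5 points on a 0-60 scale.
- A participant with three symptoms rated 3 scores 9. If each eases to 2 and a fourth appears rated 1, the score is 2 + 2 + 2 + 1 = 7. The count has risen and the score has fallen.

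**5. SAP 4.9 against 4.14.** At least 1 = exactly one + exactly two + three or more. At least 2 = exactly two + three or more. At least 3 = three or more. Each set can be derived from the other, so no information is lost, but a programmer cannot follow both layouts.

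**6. Items by sex.** The protocol gives 11 for males and 12 for females. The SAP gives 11 for females and 12 for males. Both cannot be right.

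**The case against.** The strongest reply is that worsening from 3 is not hidden from the analysis as a whole. The change in impact score has no ceiling at three symptoms, SAP 4.1 lists all collected data, and autonomic complaints reported as adverse events are tabulated by system organ class and preferred term (SAP 4.16.2). This stands. The ceiling belongs to the count table alone, and a reader who inferred that the trial could not show such worsening at all would be going too far. The score remains an incomplete substitute, because it combines number with bother and its mean change does not count people newly at 4 or more.

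It is also fair that the survey is not among the listed safety endpoints, that its summary is descriptive, and that finer tables could be produced later from the same data. This bears on severity. It is not a reason to leave the planned table as it is.

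Four further readings are tempting but not supported:

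- *Increases are missed in everyone who enters with symptoms.* Rises from 1 or 2 change category. Only entrants with exactly 3 are affected.
- *Counts from 4 upward disappear.* They are merged with 3. A participant going from 0 to 8 is counted under three or more.
- *The reversed item count inflates scores for one sex by 12/11, about 9%.* This needs the programming to expect an item that one sex is never shown and to fill it with the mean, which nothing in the documents says will happen. SAP 4.9 also leaves the symptom count unimputed, so the count table would not be inflated.
- *The six-month recall makes totals uninformative.* The recall window does reach back before Day 1 at Weeks 8 and 20, which mainly hides resolution. A newly arising symptom still raises both the count and the impact score.

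**Conclusion.** The point holds for the count table: from a baseline of exactly 3, none of the 8 (11 items) or 9 (12 items) possible rises can appear. It rests only on the entry limit and the categories as written. How much it matters depends on how many participants enter with 3, which the documents do not give. The impact score is a partial back-up. The exclusive and cumulative wordings are a layout inconsistency without loss of information. The reversal of item counts by sex is a direct contradiction; the documents do not show which version matches the questionnaire in use. Severity is minor, since this is a descriptive safety table and the data needed are already being collected.

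**What to change.** In the SAP:

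- Add a category of 4 or more to the symptom-count summary.
- Add the change from baseline in the Q1a count, or a shift table of baseline against post-baseline count, by arm and visit. Optionally add the number of participants with any new symptom, meaning an item answered No at screening and Yes at Week 8 or Week 20.
- Use one category definition in 4.9 and 4.14.
- Check the number of items for each sex against the questionnaire actually used, and correct whichever of protocol 7.9.3 and SAP 4.9 is wrong.

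The cost is SAP wording and one or two descriptive tables. No new data collection is needed.
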